Single-shot intrathecal morphine sulfate (ITM) injected while performing a spinal anesthetic for CS has been considered the gold standard for post CS pain. ITM provides analgesia for about 14-36 hours. Variable doses of ITM ranging between 50 – 250 micrograms (μ cg) have been used. Lower doses of ITM results in fewer side effects however present a tradeoff of shorter duration of analgesia.(Sutton and Carvalho 2017a) Side effects of ITM can be treated with effective prophylaxis and treatment medications. Nalbuphine and naloxone are given to treat pruritus. Nausea and vomiting are treated with ondansetron, metoclopramide, promethazine, and propofol. Respiratory depression is seen with higher doses of ITM ($\geq 150 \mu$ cg). Patients, who are obese, have obstructive sleep apnea and are on chronic pain medications or patients with opioid tolerance have a higher incidence of respiratory depression. Respiratory depression is treated with naloxone bolus followed low dose naloxone infusion. This can antagonize opioid effect and result in pain. Patients with pre-eclampsia receive magnesium, which is sedating and can further cause respiratory depression.(Sutton and Carvalho 2017a) The bimodal respiratory depression associated with ITM requires intense monitoring of respiratory status for the first 24 hours and special training for providers caring for these patients.

Eighty-one percent of all women in the US initiate breast-feeding (BF) postpartum. Early BF improves maternal-neonatal bonding. Effective pain control promotes successful BF.

A relative infant dose (RID) expressed as a percentage and is weight adjusted for the neonate (Table 1). It quantifies the amount of neonatal drug exposure relative to the mother’s dose. A value of greater than 10% is considered high. (Sutton and Carvalho 2017b) Highly protein bound drugs like non-steroidal anti-inflammatory drugs (NSAID’s) and local anesthetics (LA) have limited transfer to the neonate.

Acetaminophen provides effective analgesia PP with minimal side effects as a part of the multimodal analgesia plan (MPP). It has an opioid sparing effect of approximately 20%.

Scheduling acetaminophen for 2-3 days post CS has been recommended.(Bollag et al., n.d.)

Ibuprofen has a short half-life. RID is 0.6% in colostrum and <0.38% in mature milk. This is equivalent to 0.2% of the pediatric dose. Scheduled ibuprofen for 2-3 days has also been recommended in addition to scheduled acetaminophen. (Bollag et al., n.d.)

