Early oral intake, mobilization, removal of urinary catheter are all important components of the enhanced recovery after surgery protocol (ERAS). We hypothesize that by performing QL blocks post CS the amount of pain, narcotic consumption will be reduced significantly. Early ambulation will help prevent deep vein thrombosis. Performing QL blocks will also minimize side effects secondary to ITM and will facilitate ERAS and better patient satisfaction scores.

A recent study conducted by Salama et al concluded that QLB (without ITM) provided lower numeric rating scores at rest and during movement when compared to the group that received ITM (without QLB). Time to first morphine dose was also longer in the QLB. This study concluded that a longer duration of analgesia and reduced postoperative morphine consumption was achieved with QLB when compared to ITM.(Salama 2019)

X. Sample size

25 in each group

Total number of enrolled patients: 75

XI. Study population

Inclusion criteria

1. Age greater than 18 years
2. Elective C section via Pfannenstiel incision
3. Living singleton pregnancy
4. Gestation week at least 37 weeks
5. ASA status 1, 2 and 3

6. Primary and secondary C sections

Exclusion criteria

1. Chronic pain
2. Opioid tolerant patients
3. Allergy to drugs used in the study.
4. Cognitive dysfunction
5. BMI > 40
6. Coagulation disorder
7. Local infection
8. Inability to tolerate oral medication
9. Previous intra-abdominal surgery
10. Patients who will receive a combined spinal epidural for their C section
11. Local anesthetics injected at any other fascial plane except the QLB plane (for e.g.- local wound infiltration by surgeon)
12. Patients who received sedation or general anesthesia during their CS (midazolam, ketamine, fentanyl, propofol, hydromorphone)

Voluntary patient withdrawal from the study- patient has right to withdraw at any point during the study period

Withdrawal in case of unexpected events- This will be determined by the investigators.

XII. Primary objective

Primary objective of the study is to compare opioid consumption in morphine equivalents between the groups that received postoperative analgesia with intrathecal morphine versus US guided QL blocks versus US guided QL catheters

Our working hypothesis is-

1. Single shot QL block is equivalent to intrathecal morphine with less side effects in providing post-operative pain control for the first 24 hours.

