4. Numeric scale to rate side effects (SE) of pruritus, nausea, vomiting and sedation at 24, 48 and 72 hours; 0- no side effects 10- extremely severe side effect possible. This numeric scale is a 11-point scale as shown below. The study patient will verbally select a numerical value that best corresponds with the side effects the patient is experiencing at that point. This data will be statistically analyzed.

No SE

Distressing SE

Worst SE

No SE (0)

Mild SE (1,2,3)

Moderate SE (4,5,6)

Severe SE (7,8,9,10)

Side effects	Scale at 24 hours	Scale at 48 hours	Scale at 72 hours
Pruritus			
Nausea			
Vomiting			
Sedation			

5. Patient satisfaction will be measured on a Likert scale (5 points) at 48 and 72 hours. How satisfied were you with the following?

	Extremely satisfied	Very satisfied	Moderately satisfied	Slightly satisfied	Not satisfied
Quality of sleep					
Ability to ambulate					
Ability to breast feed/ formula feed					
Ability to take care of new born					

XIV. Study drugs

1. Preservative free morphine
2. Normal saline
3. Bupivacaine hydrochloride 0.25 %
4. Ropivacaine hydrochloride 0.1 % XV.

Study schedule

Expected start date for enrolling patients

Expected end date for enrolling patients

Enrollment period for each patient- 72 hours, earlier if discharged.

XVI. Study design

This is a prospective double-blinded randomized control trial performed at a single institution.

Screened patients meeting inclusion criteria will be randomized into three groups:

Group 1- Spinal anesthesia with ITM + US guided QLB single shot sham block + QLB catheters with no continuous infusion

Group 2- Spinal anesthesia without ITM + US guided QLB single shot with bupivacaine hydrochloride + QLB catheters with no continuous infusion

Group 3- Spinal anesthesia without ITM + US guided QLB single shot with bupivacaine hydrochloride + QLB catheters continuously infusing 0.2% ropivacaine hydrochloride

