Placement of spinal anesthesia- This will be performed by the attending anesthesiologist or anesthesiology resident who are providing anesthesia for the patient in the operating room. The anesthesia technique will be standardized. A spinal anesthetic will be performed in the sitting position at the lumbar vertebra level (L) either at L3-L4 or L4-L5 level. All women will receive a spinal anesthetic using 0.75% hyperbaric bupivacaine 912 mg plus fentanyl 20 micrograms plus epinephrine 1:100,000 100 micrograms administered intrathecally. The anesthesiologist caring for the patient will not be blinded. The anesthesiologist caring for the patient will open an opaque envelope handed to him/her by the research personnel. The envelope will clearly state the group the patient is assigned to and if ITM 200 micrograms should be added or excluded from the spinal medication. Spinal block efficacy will be considered successful if a sensory block to pinprick is achieved at a level of thoracic (T) 6 or higher. Anesthesia and surgery will be performed in the usual manner.

Placement of QL blocks- Immediately after wound closure, bilateral QL blocks will be placed by one of the investigators under direct ultrasound guidance (Sonosite X-Porte, Sonosite, Bothell, WA). For the purpose of our study we will be utilizing the QL 2 technique by Blanco to achieve blockade from T7-L1 dermatomes.(Blanco et al. 2016; Blanco, Ansari, and Grgis 2015) The anesthesiologist caring for the patient will open the opaque envelope and prepare the study drug. The study drug will either be a sham 20 ml empty syringe or 0.25% bupivacaine hydrochloride 20 ml each side. The patients will be in the supine position with a small roll of blanket placed under the ipsilateral flank. The abdomen will be cleaned with 2 % chlorhexidine gluconate and 70 % isopropyl alcohol solution (ChloraPrep® One-Step). If the patient has an allergy to any of the contents of

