The data will be analyzed within one month after completion of data collection for all enrolled patients. The deidentified data will be uploaded to PI's UTH-Share account and shared with the statistician. We will conduct Kolmogorov-Smirnov test to test normal distribution. Continuous variables will be summarized as mean and standard deviation for each group. Comparisons between any two groups will be evaluated by two-sample t test. If a variable has skewed distribution, we will report median and inter-quartile range and use Wilcoxon rank sum test for two-sample comparison. Incidences of side effects and patient satisfaction scales will be summarized as frequency and percentage for each group. Their association with intervention arm will be evaluated by Fisher's exact test. P values less than 0.05 will be considered as significant. Test and confidence interval are equivalent methods. SD is needed in calculating a confidence interval. The test is equivalent to obtaining a 90% confidence interval and comparing the upper limit of confidence interval to δ . All statistical analyses will be performed by using the SAS software (version 9.4, the SAS Institute, Cary, NC).

XX. Ethics

1. Informed consent- An informed, voluntary consent will be obtained systematically. Once the patient meets inclusion criteria, a member of our research team will speak with the patient about the study. Information will be provided regarding all study drugs, intervention and post-operative care. Standard treatment options will also be provided. Adequate time will be provided so that the patient can consult with family members, friends or look up more information using the internet.
2. Privacy and confidentiality- The patient will be linked with a study number. Only specific computers will be used by our research team to store patient information. All data will be restricted to team members, institutional review board (IRB) and FDA. Health insurance portability and accountability act (HIPPA) will be strictly followed.
3. Risk vs benefits- Major risks involved with this study are unintentional disclosure of patient information and adverse effect due to the local anesthetic leading to LAST. There is no monetary benefit involved with this study. Patient will benefit from adequate pain control with this intervention.

XXI. Study timeline

Recruitment of sample size- 9 months

Data collection and analysis- 3 months

No long-term follow up is needed with this study.

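### Side effects are first scored at 24 h and only as felt at that moment, so the plan does not measure incidence or burden over the first 24 hours, which hypothesis 1 is about

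*Combined protocol and SAP*

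**What the plan says.** Section XII, working hypothesis 1, reads: "Single shot QL block is equivalent to intrathecal morphine with less side effects in providing post-operative pain control for the first 24 hours". The side-effect part of that claim covers the same 24 hours as the analgesic part.

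The measurement is in section XIII. Item 4 of the secondary outcome measures is a "Numeric scale to rate side effects (SE) of pruritus, nausea, vomiting and sedation at 24, 48 and 72 hours". Each symptom is rated 0 to 10, and the patient picks the number that "best corresponds with the side effects the patient is experiencing at that point". The secondary objectives list the same times. The follow-up table in section XVII, item 5, also places the first side-effect rating at 24 h and lists only the pain score at 6 h and 12 h. That table stops at 48 h while section XIII goes on to 72 h, but this does not affect the first 24 hours.

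The analysis section (XIX) says: "Incidences of side effects and patient satisfaction scales will be summarized as frequency and percentage for each group". It then plans Fisher's exact test for association with arm. It does not say what score, at what time, counts as an incident case.

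**The concern.** Having fewer side effects than ITM is half of hypothesis 1 and one of the stated reasons for using the block. The hypothesis concerns a 24-hour period, but the only side-effect reading in that period is one momentary rating at its end. Such a rating gives point prevalence at hour 24. It does not give the proportion of patients who had the symptom at any time in 0-24 h, nor the severity they went through.

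The background section says these side effects are treated, for example: "Nalbuphine and naloxone are given to treat pruritus". A patient who itched or vomited at hour 5, was treated and was well by hour 24 would, as the item is worded, score 0. The treatment she received is not an outcome either. A null result could then be read as equal tolerability when it partly reflects when patients were asked. Early symptoms that were not recorded cannot be reliably recovered at analysis.

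**Working it through.** **1. Claim, measurement and analysis side by side**

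| Element | Where | Content |
|---|---|---|
| Claim | XII, hypothesis 1 | Fewer side effects, 0-24 h |
| Reading times | XIII, objectives and item 4; XVII, item 5 | First at 24 h; none at 6 h or 12 h |
| Recall period | XIII, item 4 | The moment of asking |
| Analysis | XIX | Incidence, Fisher's exact test; case not defined |

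Three sections agree on the 24 h start, so it is not a slip in one table. The claim and the analysis need a cumulative quantity, and the measurement supplies a momentary one.

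**2. The plan's own figures**

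The documents give no rate, power or sample size for side effects. The sample size for hypothesis 1 concerns opioid consumption only. Its inputs are means 27 and 10, SD 25, margin 5 and one-sided alpha 0.05. The distance from the margin is 27 − 10 + 5 = 22.

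n = 2 × 25² × (1.645 + 1.282)² / 22² = 1250 × 8.567 / 484 = 22.1, so 23 per group.

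Noncentral-t power at 23 per group is 90.2%, against 90% stated. The figure reproduces, but it neither supports nor weakens this point.

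**3. Illustration of the loss (assumed rates)**

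Let p₁ and p₂ be the true 0-24 h incidences with ITM and with block. Let f be the share of affected patients who still have the symptom at hour 24, taken as equal in both arms. The 24 h reading then compares f·p₁ with f·p₂. With n = 25 per arm,

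power = Σᵢ Σⱼ Bin(i; 25, f·p₁) · Bin(j; 25, f·p₂) · 1[two-sided Fisher p < 0.05].

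| Assumed p₁ vs p₂ | f = 1 | f = 0.75 | f = 0.50 | f = 0.25 |
|---|---|---|---|---|
| 60% vs 20% | 78.8% | 53.0% | 30.5% | 7.2% |
| 70% vs 20% | 94.6% | 74.1% | 44.6% | 12.7% |
| 50% vs 10% | 83.3% | 64.2% | 37.0% | 5.4% |

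In the first row the rates compared are 60% vs 20%, 45% vs 15%, 30% vs 10% and 15% vs 5%. The difference shrinks from 40 to 30, 20 and 10 percentage points. At 23 per arm the first row is 72.7%, 50.7%, 29.6% and 9.7%.

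**4. Direction**

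Equal f in both arms shrinks the difference. Unequal f need not. With 60% vs 20%, capturing 50% of affected ITM patients and all affected block patients gives 30% vs 20%. Capturing all in the ITM arm and 25% in the block arm gives 60% vs 5%, a difference of 55 points, wider than the true 40.

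**The case against.** Several stronger readings are tempting, and the documents do not support them.

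- *Most of the drug's action passes before the first score.* The background says "ITM provides analgesia for about 14-36 hours". Twenty-four hours is all of a 14 h duration and 24/36 = 67% of a 36 h one. But that range is stated for analgesia, and no duration is given for the four side effects. The remark that ITM "requires intense monitoring of respiratory status for the first 24 hours" concerns respiratory depression, which is not one of the scored items. The point does not need either statement, because hypothesis 1 itself names the first 24 hours.
- *The side-effect claim cannot be tested at all.* Symptoms present at hour 24 can be compared between arms. What is lost is incidence or burden over 0-24 h.
- *The comparison is biased toward no difference.* That is likely but not shown. Oral opioid is available for breakthrough pain in every arm, and the plan's planning means differ by arm and period: 27 (ITM) against 10 (single-shot block) in 0-24 h, then 29 against 49 in 24-48 h. The 49 comes from one patient. Rescue opioid could add symptoms in either arm. Low power is also not bias.
- *The 48 h and 72 h readings are misplaced.* Hypotheses 2 and 3 concern the period after 24 h, so those readings have their own purpose.

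Three defences of the plan deserve weight. First, the momentary wording is the same template as for pain, and the analysis speaks of incidences, so staff might in practice ask about the whole interval. The recall period would then be contradictory rather than firmly momentary, which still needs correcting. Second, section XVIII monitors all patients for adverse events and might catch some early symptoms. It sets no times or definitions for these four, and its examples are local anesthetic toxicity, infection and bleeding. Third, side effects are secondary outcomes, and the sample size rests on opioid use alone. This last defence stands and limits the severity.

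**Conclusion.** The concern holds in this form: as written, the plan measures symptoms present at hour 24, not incidence or burden over 0-24 h, although hypothesis 1 is about the whole period and the analysis refers to incidences. Symptoms that resolved or were treated before hour 24 are missed, and the mismatch is worst for vomiting.

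The textual finding rests on no assumption beyond following the item as worded. The size does rest on assumptions. For 60% vs 20% and 25 per arm, power goes from 79% to between 53% and 7% as the captured share falls from 75% to 25%. Both the rates and the shares are assumed, and the share is taken as equal in the two arms. The direction of any bias is likely toward no difference but not certain. The primary outcome and the opioid-based sample size are untouched, so this should be fixed but does not undermine the main analysis.

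**What to change.** 1. Ask the four side-effect items at the existing 6 h and 12 h visits as well as at the later assessments.
2. At every assessment, ask for the worst severity since the previous one, in place of severity at that moment.
3. Define 0-24 h incidence separately for each symptom, as a stated threshold reached at 6, 12 or 24 h. One option is moderate or worse on the plan's own bands (score 4 or more), with any score above 0 also reported. Pooling any nonzero score over all four symptoms could put nearly every patient in both arms above the line.
4. Name this as the measure for the side-effect part of hypothesis 1, comparing Group 2 with Group 1 by Fisher's exact test.
5. Extract charted doses given to treat pruritus, nausea or vomiting as supporting data. Exclude prophylactic doses, since the background mentions prophylaxis as well as treatment and a prophylactic dose is not an event.

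The cost is four verbal questions at two visits that already take place, a changed recall phrase and a chart extract. The small downside is reliance on short-term recall. Study treatment, visits and sample size do not change.

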2. Continuous QL catheter is more beneficial than single shot QL block or intrathecal morphine after 24 hours in providing post-operative pain control.
3. Our exploratory hypothesis is that after 48 hours a QL catheter would continue to reduce morphine consumption until 72 hours.

Primary outcome measure

Total narcotic consumption in morphine equivalents (in milligrams) for the first 72 hours after surgery will be calculated. Total narcotic used in the spinal anesthetic will be excluded.

XIII. Secondary objectives

1. Total narcotic usage at 24 and 48 hours will be assessed in morphine equivalents. Intraoperative consumption of opioids will be excluded.
2. Time to first analgesic request
3. Numeric pain score (NPS)- static and dynamic at 6, 12, 24, 48 and 72 hours
4. Pruritus at 24, 48 and 72 hours
5. Nausea at 24, 48 and 72 hours
6. Vomiting at 24, 48 and 72 hours
7. Sedation at 24, 48 and 72 hours
8. Patient satisfaction- quality of sleep, ability to ambulate, and ability to breast feed and take care of newborn at 24, 48 and 72 hours

Secondary outcome measures-

1. Total narcotic consumption in morphine equivalents (in milligrams) at 12, 24 and 48 hours will be measured.

Time after CS	Total morphine equivalents (mg)
At 4 hours	
At 6 hours	
At 12 hours	

At 24 hours	
At 72 hours	

2. Time to first analgesic request will be reviewed from the chart
3. Our research personnel will use NPS. This will be assessed at 6, 12, 24, 48 and 72 hours. NPS is a 11-point scale as shown below. The study patient will verbally select a numerical value that best corresponds with the pain the patient is experiencing at that point. This data will be statistically analyzed. Static and dynamic pain scores will be assessed. Dynamic pain scores will be assessed by asking the patient to sit up in bed from supine to sitting at 6 hours. This will be repeated at 12, 24, 48 and 72 hours however if patient is ambulating, dynamic pain score during ambulation will be assessed.

No pain

Distressing pain

Worst pain

No pain (0)

Mild pain (1,2,3)

Moderate pain (4,5,6)

Severe pain (7,8,9,10)

Time interval after CS	NPS (static)	NPS (dynamic)
At 6 hours		
At 12 hours		
At 24 hours		
At 48 hours		
At 72 hours		

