A complete pre-operative assessment will be done by the anesthesiologist or resident physician caring for the patient. Our research personnel will only evaluate patient to verify if they meet our inclusion criteria.

5. Follow up

Our research personnel who will be blinded to the study drugs used, will follow up patients.

Following data will be collected from the patient at the following time intervals.

At 6 hours	NPS		
At 12 hours	NPS		
At 24 hours	NPS	NRS for SE	
At 48 hours	NPS	NRS for SE	Likert scale for patient satisfaction

6. Termination of enrollment

Enrollment will be terminated if the following criteria are met-

- i. At the end of the 48-hour period
- ii. Intraoperative complication resulting in post-operative prolonged ventilation
- iii. Failure of neuraxial spinal anesthesia or conversion to general endotracheal anesthesia during the C section

- iv. Pfannenstiel incision converted to any other type of incision during surgery
- v. Patient death within 48 hours
- vi. Termination of study

7. Termination of study

After data collection, analysis and publication of results.

XVIII. Adverse event reporting

All patients will be monitored for adverse events. Adverse events if any will be duly documented in the research file as well as in the patient's medico legal record. All adverse events will be reported to the data safety monitoring board (DSMB). The patient will be informed of all adverse events such as local anesthetic systemic toxicity, local infection, bleeding.

XIX. Sample size and statistical analysis

Size consideration:

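### Side effects are scored only as felt at the visit, first at 24 hours, and no treatment for them is recorded, so the test of fewer side effects probably understates the difference

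*Combined protocol and SAP*

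**What the plan says.** Section XII, working hypothesis 1: "Single shot QL block is equivalent to intrathecal morphine with less side effects in providing post-operative pain control for the first 24 hours". Fewer side effects is thus part of a named hypothesis with a 24-hour window.

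Section XIII, secondary outcome measures, item 4, gives the instrument: "Numeric scale to rate side effects (SE) of pruritus, nausea, vomiting and sedation at 24, 48 and 72 hours". It also fixes the recall window: "The study patient will verbally select a numerical value that best corresponds with the side effects the patient is experiencing at that point". That is the current state, not the worst or any occurrence since surgery.

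The background expects these effects to be treated: "Side effects of ITM can be treated with effective prophylaxis and treatment medications". It continues: "Nalbuphine and naloxone are given to treat pruritus", and "Nausea and vomiting are treated with ondansetron, metoclopramide, promethazine, and propofol". It names no drug for sedation.

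Section XVII, item 5 (Follow up) opens its table with "Following data will be collected from the patient at the following time intervals". The table holds pain scores, side-effect scores and satisfaction. Neither it nor the section XIII outcome list includes any drug given for a side effect. The medication data planned are opioid use and time to first analgesic request, the latter taken from the chart.

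The statistical analysis plan in section XIX summarises side-effect incidences as counts and percentages and tests them with Fisher's exact test. It does not say which score makes a case or how a treated patient is classified.

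**The concern.** The hypothesis is about what happens over the first 24 hours. The measurement is a snapshot at the end of them. A patient who itches at 8 hours, is treated and is comfortable at 24 hours scores 0 and counts as never affected. So does a patient whose nausea passed without treatment at 10 hours.

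On the protocol's own premise, ITM causes more of these effects, so more patients are lost from the count in group 1 than in group 2. The contrast the trial wants to show would then be understated. A null result could not be read: it might mean no difference in side effects, or a difference that treatment and time had removed before anyone asked.

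**Working it through.** **1. The plan's own figures.** The only stated sizes concern opioid use, and they reproduce.
- Hypothesis 1: means 10 and 27, SD 25, margin 5, one-sided 0.05. Distance to the margin = 5 − (10 − 27) = 22. Standard error at 23 per group = 25 × √(2/23) = 7.37. The noncentral t gives 90.2% power (plan: 90%).
- Hypothesis 2: 49 − 20 = 29, SD 23, two-sided 0.05. Power is 91.5% at 15 per group (plan: 91.5%) and 98.7% at 23.
- Both: 0.902 × 0.987 = 0.890 (plan: 89.4% by simulation).

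None of these covers side effects. The documents give no side-effect rate, effect size or power.

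**2. Direction.** Let p be the true share of patients affected by 24 hours, and f the share of those who score 0 at the visit because the episode was treated or had resolved. The observed rate is p(1 − f), so

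observed difference = (p_ITM − p_QL) − (p_ITM × f_ITM − p_QL × f_QL).

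The difference shrinks whenever p_ITM × f_ITM exceeds p_QL × f_QL. That holds if ITM causes more side effects and its affected patients are masked at least as often. With an equal f in both arms, the difference is multiplied by (1 − f). At 60% and 20%, f in the block arm would have to be more than 0.60/0.20 = 3 times that in the ITM arm for the difference to widen.

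**3. Illustration of size.** The 23 per arm and the 0.05 level come from section XIX. The rates and f are assumptions. A case is taken to be any score above 0, since the plan sets no cut-off. Power is exact: the sum of Bin(i; 23, a) × Bin(j; 23, b) over all tables (i, j) with two-sided Fisher p below 0.05.

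Assumed truth 60% (ITM) and 20% (block), same f in both arms:
- f = 0: 60% vs 20%, difference 40 points, power 72.7%
- f = 25%: 45% vs 15%, difference 30 points, power 50.7%
- f = 50%: 30% vs 10%, difference 20 points, power 29.6%
- f = 75%: 15% vs 5%, difference 10 points, power 9.7%

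**4. Sensitivity to the assumed ITM rate**, from 50% to 70% with the block at 20%:
- f = 0: power 46.2% to 91.3%
- f = 25% in both arms: 31.0% to 70.0%
- f = 50% in both arms: 17.8% to 43.3%

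**The case against.** Several counter-arguments deserve weight.

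- **Symptom burden under usual care is a legitimate outcome.** True, and the raw score should stay. But the hypothesis says fewer side effects and section XIX speaks of incidences, and a snapshot after treatment measures neither over 24 hours.
- **The bias works against the sponsor's hypothesis.** It should not create a false claim of fewer side effects. This limits the consequence to a missed or diluted finding on a secondary outcome that was not powered.
- **The data may not be lost.** Treatments are probably in the chart, and section XVIII asks for adverse events to be documented. But its examples are local anesthetic toxicity, infection and bleeding, and nothing links either source to this comparison.
- **The illustration is only that.** The rates are invented, and partial relief to a score of 1 to 3 would still count as a case above 0. Both points stand.

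A reader might also infer more than the documents support.

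- **That treatment occurs only in the ITM arm.** With half of affected ITM patients masked and no block patients, the contrast becomes 30% vs 20% and power 7.3%. Nothing suggests that affected block patients would go untreated.
- **That all four side effects are masked by treatment.** No drug is named for sedation, so that mechanism is not shown there.
- **That better contact could not help.** Visits already exist at 6 and 12 hours, and asking for the worst symptom since the last visit would capture much of what is lost, including untreated episodes.
- **That nalbuphine given for itch inflates the ITM opioid total and eases non-inferiority.** The documents give no nalbuphine dose, frequency or conversion and never say it will be counted; the postoperative opioids they provide for are oxycodone and hydromorphone. Nor is the spinal opioid ("Total narcotic used in the spinal anesthetic will be excluded") the sole exclusion: section XIII, secondary objective 1, also removes intraoperative opioids from the 24- and 48-hour totals. What remains is a missing sentence on postoperative nalbuphine, with no size that can be put on it.

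**Conclusion.** The concern holds for pruritus, nausea and vomiting. As planned, episodes treated or resolved before the 24-hour visit can count as no side effect, and neither a recall question nor a treatment record recovers them.

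That the difference is pulled towards zero is an inference. It rests on the protocol's premise that ITM causes more of these effects, and on affected ITM patients being masked at least as often as affected block patients. The size cannot be derived from the documents. Under the assumed 60% and 20%, masking a quarter to a half of cases in both arms cuts power from about 73% to between 51% and 30%. The opioid sample size is unaffected.

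**What to change.** 1. **Treatment record.** For each period (0–24, 24–48 and 48–72 hours), extract from the chart whether antipruritic, antiemetic or opioid-antagonist treatment was given, the number of doses and the indication. The indication matters because the background also lists naloxone for respiratory depression, and because routine prophylaxis should not count as an event. The follow-up table stops at 48 hours while section XIII goes to 72, so the two need to be reconciled for the third period.
2. **Recall window.** In section XIII, item 4, ask for the worst symptom since the last visit.
3. **Case definition.** In section XIX, define pruritus, nausea and vomiting each as present in a period if the score is above 0 or treatment for it was given. Compare that by arm, and report the raw score and the proportion treated alongside. Sedation keeps the score alone.
4. **Minor clarification.** State under the primary outcome measure and the 24- and 48-hour totals that postoperative nalbuphine or naloxone given for side effects is not counted in morphine equivalents.

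The cost is one case-report line per period from a chart already being reviewed, one reworded question and a few sentences. Care and sample size do not change. A small downside is that treatment use also reflects staff prescribing habits, which is why the raw score should be shown too.
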